### 8.2.1.2. Statistical Analysis

Bayesian analysis for binary endpoint	
Endpoints	Endoscopic Mucosal Healing (Endoscopic Improvement)
Statistical analysis	Logistic regression
Predictors	
 
• TRT = study treatment(categorical)
 
• Advanced Therapy Experience (categorical)
 
• Baseline Adapted Mayo (continuous)
 
• Duration of disease, years (continuous)
 

Model	$y_i \sim \text{Ber}(p_i)$ $\text{logit}(p_i) = (\text{TRT}=\text{Placebo}) \times \beta_1 + (\text{TRT}=450\text{mg}) \times \beta_2 + (\text{Duration}^*) \times \beta_3 + (\text{Baseline}^*) \times \beta_4 + (\text{Experience}^*) \times \beta_5$
Outcome	$y_i = \text{response (0/1) for participant } i$
Population-level coefficients ( $\beta$ )	
 
• <math>\beta</math> = fixed effects, parameters associated to predictors  <math>\beta_1</math> : informative prior distribution,  <math>\text{logit}^{-1}(\beta_1) \sim \text{mixture of Betas}^{**}</math>
 
<math>\beta_2</math> : non-informative prior distribution,  <math>\text{logit}^{-1}(\beta_2) \sim \text{Beta}(1/3, 1/3)</math>
 
<math>\beta_k</math> for other predictors: non-informative prior distributions,  <math>\beta_k \sim \text{Normal}(\text{mean}=0, \text{SD}=100)</math>
 

\* Unless otherwise specified the predictors (not including study treatment) will be centred around their estimated mean in the model

\*\* The parameterisation of the priors used in the analysis will be described in [Appendix 14](#): Details of the Informative Placebo Prior and reported in the clinical study report

Further details of key secondary analysis	
Overview of approach	
	
For interim 2 and 3 the predictive probability of meeting the end of study success criteria will be assessed after the Week 10 endoscopy (or withdrawal) has been observed on the number of participants specified for that data cut.
 
A sample from the posterior distribution of the difference in response rates between each treatment arm and placebo will be obtained using Markov chain Monte Carlo (MCMC). This analysis will account for historical placebo data by using an informative prior distribution for the placebo arm and a vague Beta (1/3,1/3) distribution for the active arm (Kerman, 2011).

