	
 
○ Strategy: hypothetical, setting response status to missing.
 
○ ICE: valid endoscopy result not available, for technical reasons
 
○ Strategy: hypothetical, setting response status to missing.
 
○ ICE: prohibited medication taken
 
○ Strategy: included in outcome via composite strategy (i.e. post-ICE result set to non-response).
 
○ ICE: increase in dose of permitted medications
 
○ Strategy: included in outcome via composite strategy (i.e. post-ICE result set to non-response).
 
● Population-level summary: Difference in proportion of participants who achieve response between placebo and relevant active doses
 

Estimation and missing data details for the key secondary estimand for decision making (“Composite”)	
	
Participants who have a missing assessment at Week 10 for reasons unrelated to the COVID-19 pandemic will be counted as non-responders in the analysis.
 
The ICEs that will be dealt with using a hypothetical strategy will have response status set to missing
 
In all cases, the missing response status will be assumed to be MAR in the statistical analysis.
 
The MAR assumption is implicit in the planned Bayesian analysis.

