### Informative Placebo Prior

- The prior distribution is a robust mixture prior based on historical data following the approach of ([Schmidli, 2014](#)). A meta analytic predictive (MAP) prior of relevant historical data is created, with a covariate for the proportion of Advanced Therapy Experienced in each historical trial.
- The MAP prior is obtained via an MCMC model with the following specifications:
  - For each historical trial  $s$  with  $r$  responders in  $N$  placebo patients and percentage of Advanced Therapy Experienced  $\%Exp$ :
 
$$r_s \sim \text{Binomial}(\text{size} = N_s, \text{rate} = \text{rate}_s)$$

$$\text{rate}_s = \text{logit}^{-1}(\alpha + \beta * \%Exp_s + \epsilon_s)$$

$$\epsilon_s \sim \text{Normal}(0, \tau)$$
  - Prior for between-trial heterogeneity  $\tau$ : half-normal with  $\mu=0$ ,  $\sigma=z/2$  where  $z$  is derived via the  $n\infty$  method ([Neuenschwander., 2010](#)):
    - $p$  = mean of  $r/N$  of historical trials
    - $z = [\sqrt{p^*(1-p)}]^{-1}$
  - Priors for coefficients  $\alpha, \beta$ : normal with  $\mu=0$ ,  $\sigma=100$
- The MCMC samples of the placebo response are approximated using appropriate parametric distributions, typically a mixture of two to three Beta distributions. Unless stated otherwise, the number of Beta distributions in the mixture is decided via AIC.
- The prior used for analysis will use the proportion of Advanced Therapy Experienced participants observed in this trial at the relevant interim or final analysis.
- The rules for including historical data used for this analysis will be documented in [Appendix 14: Details of the Informative Placebo Prior](#).
- The MAP prior distribution is 'robustified' by further mixing with a non-informative Beta(1/2,1/2) distribution with 40% weight for the non-informative prior.
- The final prior distribution and supporting information will be documented in the trial master file before the study is unblinded for interim analysis 3.
- Examples of the parametric distributions used at different levels of the covariate are documented in [Appendix 14: Details of the Informative Placebo Prior](#).

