### Model Results Presentation

- At IA3, the predictive probability that the end of study success will be achieved according to specific thresholds will be displayed (thresholds will be specified in the programming notes for this output).
    - The predictive probability of end of study success is obtained by simulating 10,000 trials
    - In each simulated trial, post-IA3 Endoscopic Improvement results for Placebo and 450mg are simulated using the posterior samples for the response rates obtained in the MCMC model at IA3. The IA3 Endoscopic Improvement counts for Placebo and 450mg are summed to the simulated post-IA3 data to obtain simulated results for the full study.
    - In each simulated trial, end of study success is calculated using the posterior distributions for 450mg and Placebo (without covariates):
      - In the Active arm, a non-informative Beta(1/3,1/3) is used as prior.
      - In the Placebo arm, the MAP prior described above (an informative mixture of Betas) is used as prior.
      - The mixture Placebo prior will take the following form:
$$\sum_{k=1}^K w_k * Beta(a_k, b_k)$$
    - When computing the Placebo posterior using simulated results ( $r1$  responders out of  $n1$  participant) each of the  $k$  mixture components takes the following form (Röver, 2020):
- $$w_k * \binom{n1}{r1} * \frac{\Gamma(a_k + b_k)\Gamma(a_k + r1)\Gamma(b_k + n1 - r1)}{\Gamma(a_k)\Gamma(b_k)\Gamma(n1 + a_k + b_k)} * Beta(a_k + r1, b_k + n1 - r1)$$
- The posterior distribution of each arm and the treatment difference will be summarized using mean and equal-tailed 95% credible region and the probability of being above specific thresholds specified in the programming notes for this output.
  - Posterior density plots will be available in model output but will not be presented.

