#### 8.2.2. Other Secondary Endpoints - Categorical

The ICE strategy for the Key Secondary Estimand described in Section 8.2.1.1 above will be replicated in the following secondary Efficacy endpoints:

Endpoint	Endpoint name to be displayed for Estimand Analysis
Adapted Mayo Clinical Remission at Week 10	Secondary – Adapted Mayo Clinical Remission
Adapted Mayo Clinical Response at Week 10	Secondary – Adapted Mayo Clinical Response
Symptomatic Remission at Week 10	Secondary – Symptomatic Remission

The “Secondary Estimand – Clinical Remission” will be analysed by replicating the statistical model described in Section 8.2.1.2 above. The other two estimands in the table above will be summarised only.

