
Do include Complete Mayo clinical remission.
 
Endoscopic Improvement
 
Use endoscopic score of 0 or 1. Where available, use 'adapted Mayo' endoscopic score (where any CCI [REDACTED] is a score of [REDACTED])
	
modified/adapted Mayo definition will be used as will a definition that includes RB=0 which is consistent with the criterion used in 204869.
 
Endoscopic Improvement
 
This definition has changed over the period in scope, with historical trials using a slightly different definition of endoscopic score, this data will still be used, where multiple scores are available for a study the modified/adapted Mayo definition will be used.

Note that the data used for the placebo priors will be extracted from the Certara clinical outcomes database for Ulcerative Colitis which includes data from abstracts and scientific posters as well as published scientific articles.
 
Note that only studies where the placebo response rate can be calculated from the number of placebo responders and the total number of participants in the placebo arm will be used. No strata are used, to resolve duplicates where appropriate the results from the primary statistical analysis is used.
	

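### The key secondary logistic model yields response rates at average covariates, not the estimand's proportions of participants: a cheap estimation fix that matters mainly for clinical remission

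*SAP*

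**What the plan says.** The population-level summary of the key secondary estimand (SAP 8.2.1.1) is "Difference in proportion of participants who achieve response between placebo and relevant active doses".

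The model in SAP 8.2.1.2 is a logistic regression without an intercept: one coefficient for placebo (β1), one for 450 mg (β2), plus terms for disease duration, baseline Adapted Mayo and advanced therapy experience. On those three it says: "Unless otherwise specified the predictors (not including study treatment) will be centred around their estimated mean in the model". The priors sit on inverse-logit(β1) and inverse-logit(β2) and are described as "using an informative prior distribution for the placebo arm" and "a vague Beta (1/3,1/3) distribution for the active arm". The results paragraph then summarises the posterior of each arm and of the difference by mean, 95% credible region and threshold probabilities.

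Three further passages bear on the point:
- SAP 8.2.2 says clinical remission "will be analysed by replicating the statistical model described in Section 8.2.1.2 above".
- Post-IA3 data are "simulated using the posterior samples for the response rates obtained in the MCMC model at IA3".
- Appendix 14 restricts the historical trials to those whose "placebo response rate can be calculated from the number of placebo responders and the total number of participants in the placebo arm", so the placebo prior starts from trial-level proportions. It is then mixed with "40% weight for the non-informative prior".

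Nowhere does the SAP say that predicted probabilities are averaged over participants before they are reported.

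**The concern.** With centred covariates, inverse-logit(β1) and inverse-logit(β2) are response probabilities for a participant whose covariates all equal the trial mean. The logit link is not linear, so this is not the proportion of participants who respond. For rates below 50% it generally lies lower, and by more when the covariates are more prognostic.

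If these are the reported rates, the model output answers a different question from the estimand. Table 2.21 and Figure 2.7 would disagree with the observed and estimand-imputed proportions in Tables 2.17 and 2.28, with nothing in the SAP to explain it. For a low-rate endpoint such as remission, the difference itself could be too small and its interval too narrow.

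**Working it through.** **The plan's own figure.** The only operating characteristic given for the binary endpoint is a probability above 80% of stopping at IA3 if placebo response is 20% and there is no effect (Protocol 9.2.1). It cannot be reproduced, because the futility rule is in the DRC charter.

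**Inputs from the documents.** Placebo endoscopic response 20%; 20 v 40 (placebo v 450 mg) at IA3 and 48 v 68 at the planned final analysis (Protocol 9.2.1); priors from SAP 8.2.1.2. The experience effect is read from the main historical components in Appendix 14: Beta(3,20) at 20% naive and Beta(4,13) at 80% naive. The implied log odds ratio, naive v experienced, is [ln(4/13) − ln(3/20)] / (0.80 − 0.20) = 0.718 / 0.60 ≈ 1.2. This is an ecological reading.

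**Assumed inputs.** 40% target response on 450 mg for the endoscopic endpoint; 60% experienced; remission rates of 5% v 15%; remission placebo prior 40% Beta(1/2,1/2) + 60% Beta(1.5,25); baseline and duration effects from none to strong.

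**Step 1: gap without sampling error, experience effect only.** Centred, experienced participants sit at −0.48 and naive at +0.72. Find b with 0.6·expit(b − 0.48) + 0.4·expit(b + 0.72) = p, and report expit(b).
- p = 20%: b = −1.490 gives 0.6 × 0.1224 + 0.4 × 0.3165 = 0.200, and expit(b) = 18.4%.
- p = 40% becomes 39.3%, 15% becomes 13.5%, 5% becomes 4.3%.

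The endoscopic difference becomes 39.3 − 18.4 = 20.9 points (true 20). The remission difference becomes 13.5 − 4.3 = 9.2 points (true 10). With moderate covariates (linear predictor SD 0.78 rather than 0.59), 20% becomes 17.4%, 15% becomes 12.6% and 5% becomes 3.9%.

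**Step 2: simulation of the SAP model.** 1,000 trials per scenario were fitted by MCMC. The same posterior was summarised in two ways: inverse-logit(β2) − inverse-logit(β1) (centred), and the average of the inverse-logit over participants' covariates (standardised). The Monte Carlo standard error of coverage is about 1 point. Rates are placebo/450 mg in %; bias is in points.

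| Scenario | Summary | Rates | Bias | Coverage | Width |
|---|---|---|---|---|---|
| Endoscopic 20 v 40, moderate, 48 v 68 | centred | 16.7/38.0 | +1.3 | 93.7% | 0.308 |
| | standardised | 20.6/40.0 | −0.5 | 94.7% | 0.280 |
| Endoscopic 20 v 40, moderate, 20 v 40 | centred | 16.3/37.7 | +1.4 | 95.2% | 0.420 |
| | standardised | 21.2/40.3 | −0.9 | 95.6% | 0.371 |
| Remission 5 v 15, experience only, 48 v 68 | centred | 4.0/11.8 | −2.2 | 88.6% | 0.171 |
| | standardised | 5.9/15.5 | −0.4 | 94.6% | 0.195 |
| Remission 5 v 15, moderate, 48 v 68 | centred | 3.8/11.1 | −2.7 | 86.5% | 0.166 |
| | standardised | 6.1/15.4 | −0.7 | 94.0% | 0.194 |
| Remission 5 v 15, moderate, 20 v 40 | centred | 3.9/9.9 | −4.0 | 83.6% | 0.213 |
| | standardised | 7.7/15.7 | −2.1 | 93.4% | 0.266 |

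The endoscopic interval at 48 v 68 is 0.308/0.280 = 1.10 times as wide when centred.

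**Step 3: range and cross-check.**
- Strong covariates (SD 1.35), remission at 48 v 68: coverage 74.8% centred, 93.3% standardised.
- No true covariate effect, remission at 20 v 40: 89.0% centred, 95.6% standardised. Over-fitted coefficients under the N(0, SD 100) priors push the centred rate down on their own.
- A vague placebo prior, moderate covariates, at 48 v 68: 85.8% centred, so the informative prior is not the cause.
- A second simulation (600 trials, 48 v 68) gave remission bias of −2.2 to −2.5 points and coverage of 88–89% centred, against about −0.6 points and 95–96% standardised. Endoscopic rates were 16.4%/38.2% (width 0.312) against 20.0%/40.0% (width 0.283).

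**Step 4: false positives.** With no effect and moderate covariates at 48 v 68, the interval lies above zero in 2.1% of trials either way (endoscopic 20% v 20%) and in 1.4% either way (remission 5% v 5%). With a true effect the shares also match: 76.6% and 76.6% for 20% v 40%, 48.8% and 49.0% for 5% v 15%.

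**The case against.** The strongest objection is that the SAP never writes that inverse-logit(β) is what gets reported. Table 2.21 and Figure 2.7 also call for estimates by level of advanced therapy experience, so the code must evaluate the model away from mean experience. The shells are in a separate document and the thresholds are in programming notes. This stands: the reading is an inference from the parameterisation and from where the priors sit. But rates by experience level at mean baseline and duration would still not be proportions of participants, and the step from model to estimand is unspecified either way.

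Second, a reader might infer that the declared decision endpoint is seriously biased. The figures do not support that: the endoscopic difference is off by under 2 points with near-nominal coverage. What suffers is the two arm rates and the precision.

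Third, the remission harm rests on rates, a prior and covariate effects that the documents do not give. In a separate run of 300 trials per scenario at 6% v 16% with weaker covariates (odds ratios 0.5 and 0.7), centred coverage was 93% with bias of −1.6 points. At that number of trials 93% is not clearly below nominal. At 20 v 40, standardising also leaves about half of the −4.0 point bias: the 450 mg rate is about right, but the placebo rate is estimated at 7.7% against a true 5%. Both stand, so the size is conditional.

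Fourth, observed and estimand-imputed proportions are already planned beside the model output (Tables 2.17 and 2.28, Figures 2.6 and 2.9). That limits the risk of misreading but does not correct the model-based difference or its interval.

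Finally, a lower rate at the mean is usual below 50% but not universal. With a linear predictor of −0.6 (probability 0.9) and +4.4 (probability 0.1), the rate at the mean is 47.5% and the average rate is 41.8%.

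**Conclusion.** The point holds as an improvement to estimation. Followed as written, 8.2.1.2 most naturally reports rates at average covariates while the estimand is a difference in proportions. Endoscopic arm rates would be understated by roughly 2 to 4 points, with the difference nearly unbiased and its interval about 10% too wide. For remission, a true 5% v 15% would be understated by about 2 to 3 points at 48 v 68, with coverage of about 86–89% under experience-only or moderate covariates, worse with stronger effects and better with weaker ones. This rests on the inferred reading and on the assumed remission rates, prior and covariate effects.

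Two stronger readings are tempting and should be resisted. One is that the method inflates false positives: intervals exclude zero equally often either way. The other is that it distorts the IA3 futility decision. The simulated future counts would come from these rates, but end-of-study success is judged without covariates on counts that include the actual IA3 data. The study was also terminated on 14-JAN-2021, before this SAP was approved, so no continuation decision now depends on it.

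**What to change.** Add to SAP 8.2.1.2, and through it 8.2.2:

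- For each MCMC draw, compute the response rate under each treatment as the average of the inverse-logit over the observed covariates of all 450 mg and placebo participants.
- Derive the arm rates, the difference and the threshold probabilities from these averages.
- Say how the by-experience estimates in Table 2.21 and Figure 2.7 are averaged.
- If any predictive simulation is still run, generate its data from the same standardised rates.

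The model and priors may stay. The SAP should note that the historical placebo prior, built from trial-level proportions, is then only approximately on the scale of the average-covariate rate on which it is placed; standardising does not remove that mismatch.

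The cost is one SAP paragraph and a few lines of post-processing. Reported rates will shift slightly from those of the current code, unless it already standardises, in which case only the sentence is needed.

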### Informative Placebo Prior

- The prior distribution is a robust mixture prior based on historical data following the approach of ([Schmidli, 2014](#)). A meta analytic predictive (MAP) prior of relevant historical data is created, with a covariate for the proportion of Advanced Therapy Experienced in each historical trial.
- The MAP prior is obtained via an MCMC model with the following specifications:
  - For each historical trial  $s$  with  $r$  responders in  $N$  placebo patients and percentage of Advanced Therapy Experienced  $\%Exp$ :
 
$$r_s \sim \text{Binomial}(\text{size} = N_s, \text{rate} = \text{rate}_s)$$

$$\text{rate}_s = \text{logit}^{-1}(\alpha + \beta * \%Exp_s + \epsilon_s)$$

$$\epsilon_s \sim \text{Normal}(0, \tau)$$
  - Prior for between-trial heterogeneity  $\tau$ : half-normal with  $\mu=0$ ,  $\sigma=z/2$  where  $z$  is derived via the  $n\infty$  method ([Neuenschwander., 2010](#)):
    - $p$  = mean of  $r/N$  of historical trials
    - $z = [\sqrt{p^*(1-p)}]^{-1}$
  - Priors for coefficients  $\alpha, \beta$ : normal with  $\mu=0$ ,  $\sigma=100$
- The MCMC samples of the placebo response are approximated using appropriate parametric distributions, typically a mixture of two to three Beta distributions. Unless stated otherwise, the number of Beta distributions in the mixture is decided via AIC.
- The prior used for analysis will use the proportion of Advanced Therapy Experienced participants observed in this trial at the relevant interim or final analysis.
- The rules for including historical data used for this analysis will be documented in [Appendix 14: Details of the Informative Placebo Prior](#).
- The MAP prior distribution is 'robustified' by further mixing with a non-informative Beta(1/2,1/2) distribution with 40% weight for the non-informative prior.
- The final prior distribution and supporting information will be documented in the trial master file before the study is unblinded for interim analysis 3.
- Examples of the parametric distributions used at different levels of the covariate are documented in [Appendix 14: Details of the Informative Placebo Prior](#).

### Model Checking & Diagnostics

- Each chain will initially have length 0f 1,000,000, thin of 10 and burn-in length of 50,000.
- Chain convergence diagnostics will be saved in HARP (refdata folder) and inspected.
- The MCSE will be compared with the standard deviation of the posterior distribution (SD) to ensure that only a fraction of the posterior variability is due to simulation error, i.e., the ratio MCSE/SD should be close to 0.01

### Model Results Presentation

- At IA3, the predictive probability that the end of study success will be achieved according to specific thresholds will be displayed (thresholds will be specified in the programming notes for this output).
    - The predictive probability of end of study success is obtained by simulating 10,000 trials
    - In each simulated trial, post-IA3 Endoscopic Improvement results for Placebo and 450mg are simulated using the posterior samples for the response rates obtained in the MCMC model at IA3. The IA3 Endoscopic Improvement counts for Placebo and 450mg are summed to the simulated post-IA3 data to obtain simulated results for the full study.
    - In each simulated trial, end of study success is calculated using the posterior distributions for 450mg and Placebo (without covariates):
      - In the Active arm, a non-informative Beta(1/3,1/3) is used as prior.
      - In the Placebo arm, the MAP prior described above (an informative mixture of Betas) is used as prior.
      - The mixture Placebo prior will take the following form:
$$\sum_{k=1}^K w_k * Beta(a_k, b_k)$$
    - When computing the Placebo posterior using simulated results ( $r1$  responders out of  $n1$  participant) each of the  $k$  mixture components takes the following form (Röver, 2020):
- $$w_k * \binom{n1}{r1} * \frac{\Gamma(a_k + b_k)\Gamma(a_k + r1)\Gamma(b_k + n1 - r1)}{\Gamma(a_k)\Gamma(b_k)\Gamma(n1 + a_k + b_k)} * Beta(a_k + r1, b_k + n1 - r1)$$
- The posterior distribution of each arm and the treatment difference will be summarized using mean and equal-tailed 95% credible region and the probability of being above specific thresholds specified in the programming notes for this output.
  - Posterior density plots will be available in model output but will not be presented.

